2. INTRODUCTION

CCI

The purpose of the proposed Phase 2 study in older adults is to assess the safety, tolerability, and immunogenicity of 20vPnC and to generate a safety and immunogenicity data set with 20vPnC to support and inform the design of the Phase 3 clinical development program for adults.

2.1. Study Objectives

The primary objective of this study is to describe the safety profile of 20vPnC in the study population.

The secondary objective of this study is to describe the immunogenicity of 20vPnC in the study population. CCI

2.2. Study Design

This is a Phase 2, multicenter, randomized, active-controlled, double-blind study with a 2-arm parallel design. A total of 440 adults 60 through 64 years of age with no history of pneumococcal vaccination will be enrolled and randomized equally to receive either

- a single dose of 20vPnC followed 1 month later by saline (placebo) administration (20vPnC/saline group), or

- a single dose of 13vPnC followed 1 month later by a dose of 23-valent pneumococcal polysaccharide vaccine (PPSV23) (13vPnC/PPSV23 group). This is the control group.

13vPnC will serve as a control for safety, as well as immunogenicity of the 13 serotypes in common with 20vPnC. PPSV23 will serve as a control for immunogenicity of the 7 additional serotypes (8, 10A, 11A, 12F, 15B, 22F, and 33F) in 20vPnC.

Table 1. Time Points for Key Safety and Immunogenicity Objectives by Investigational Product

	20vPnC	Control – 13vPnC ^a	Control – PPSV23 ^b
Prompted local reactions	X (10 days after Visit 1)	X (10 days after Visit 1)	
Prompted systemic events	X (7 days after Visit 1)	X (7 days after Visit 1)	
Adverse events ^c	X (1 month after Visits 1 and 2)	X (1 month after Visit 1)	X (1 month after Visit 2)
Immune responses to serotypes in common with 13vPnC: 1, 3, 4, 5, 6A, 6B, 7F, 9V, 14, 18C, 19A, 19F, 23F	X (1 month after Visit 1)	X (1 month after Visit 1)	
Immune responses to additional 7 serotypes: 8, 10A, 11A, 12F, 15B, 22F, 33F	X (1 month after Visit 1)		X (1 month after Visit 2)

- a. Control group from enrollment and vaccination with 13vPnC at Visit 1 until vaccination with PPSV23 at Visit 2.
- b. Control group after vaccination with PPSV23 at Visit 2.
- c. SAEs and newly diagnosed chronic medical conditions (NDCMCs) will be collected through Visit 5 (12 months after Visit 1).

Blood samples will be collected on the day of investigational product administration prior to each vaccination (Vaccination 1 and Vaccination 2), 1 month after Vaccination 2, and 12 months after Vaccination 1 [REDACTED]. Prompted local reactions at the injection site and prompted systemic events will be collected daily for 10 and 7 days, respectively, after Vaccination 1. Adverse events (AEs) occurring from signed informed consent through 1 month after Vaccination 2 will be collected and serious adverse events (SAEs) and newly diagnosed chronic medical conditions (NDCMCs) will be collected through 12 months after Vaccination 1.

CCI

3. ENDPOINTS AND BASELINE VARIABLES: DEFINITIONS AND CONVENTIONS

3.1. Primary Endpoints

The primary and secondary endpoints pertain to the 20vPnC vaccination (Vaccination 1), as described in the objectives, along with the applicable control group and time point (see [Table 1](#)).

- Proportions of subjects reporting prompted local reactions within 10 days after Vaccination 1 (redness, swelling, and pain at the injection site).
- Proportions of subjects reporting prompted systemic events within 7 days after Vaccination 1 (fever, headache, fatigue, muscle pain, and joint pain).
- Proportions of subjects reporting AEs within 1 month after Vaccination 1.
- Proportions of subjects reporting SAEs and NDCMCs within 6 months and 12 months after Vaccination 1.

3.2. Secondary Endpoint(s)

- Pneumococcal serotype-specific opsonophagocytic activity (OPA) geometric mean titers (GMTs) 1 month after Vaccination 1. See [Table 1](#) for the applicable control group and time point for each serotype.
- Pneumococcal serotype-specific OPA geometric mean fold rises (GMFRs) from before Vaccination 1 to 1 month after Vaccination 1. See [Table 1](#) for the applicable control group and time point for each serotype.

3.3. Other Endpoints

CCI

CCI

[figure not shown]

3.3.1. Local Reactions

The local reactions assessed and reported in the electronic diary (e-diary) are redness, swelling, and pain at the injection site, from Day 1 through Day 10, where Day 1 is the day of Vaccination 1.

Severity and Maximum Severity

Redness and swelling will be measured and recorded in measuring device units (range: 1 to 21+), and then categorized during analysis as mild, moderate, or severe based on the grading scale in [Table 2](#) below. Measuring device units will be converted to centimeters according to the following scale: 1 measuring device unit = 0.5 cm. Reactions smaller than 5 measuring device units (<2.5 cm) will be scored as “none,” but such values will still be reported in the listings. Pain at the vaccine injection site will be assessed by the subject as mild, moderate, or severe according to the grading scale in [Table 2](#).

For each local reaction, the maximum severity grade will be derived for the e-diary collection period (Day 1 to Day 10, where Day 1 is the day of Vaccination 1) as follows:

- = missing, if all values are missing for Day 1 to Day 10;
- = 0, if the subject reports all reactions as “no” or a combination of missing and “no” for all Days 1 to 10;
- = highest grade (maximum severity) within 10 days of Vaccination 1 (Day 1 to Day 10) among severity grades where the answers are neither “no” nor missing for at least 1 day during Days 1 to 10.

Note that Grade 4 severity will not be collected in the e-diary but will be collected as an AE on the case report form (CRF).

Table 2. Grading Scales for Local Reactions

	Mild Grade 1	Moderate Grade 2	Severe Grade 3	Grade 4
Redness (erythema)	5 to 10 measuring device units = 2.5 to 5.0 cm	11 to 20 measuring device units = 5.5 to 10.0 cm	≥21 measuring device units = ≥10.5 cm	Necrosis or exfoliative dermatitis
Swelling (edema)	5 to 10 measuring device units = 2.5 to 5.0 cm	11 to 20 measuring device units = 5.5 to 10.0 cm	≥21 measuring device units = ≥10.5 cm	Necrosis
Pain at injection site	Does not interfere with activity	Interferes with activity	Prevents daily activity	Emergency room visit or hospitalization

Abbreviations: e-diary = electronic diary.

Note: If the size of the redness and/or swelling falls between 2 measuring device units, the higher measuring device unit number will be recorded in the e-diary.

Presence or Absence

For the data summary of the presence (yes or no) of a local reaction during Day 1 to Day 10, where Day 1 is the day of Vaccination 1, the following variables are required:

- Maximum severity of each local reaction on any day (Day 1 to Day 10);
- Presence (yes or no) of each local reaction on each day (Day 1 to Day 10);
- Presence (yes or no) of each local reaction on any day (Day 1 to Day 10);
- Presence (yes or no) of any local reaction on each day (Day 1 to Day 10);

- Presence (yes or no) of any local reaction on any day (Day 1 to Day 10);
- Presence (yes or no) of each severe (Grade 3, as defined in [Table 2](#)) local reaction on each day and any day (Day 1 to Day 10);
- Duration of each local reaction (duration will be calculated both from first to last day and also as total days with the indicated event);
- Onset day of each local reaction;
- **CCI** [REDACTED]

For each local reaction on any day, Table 3 below explains the algorithm to derive the presence of a reaction (yes or no) during Day 1 to Day 10, where Day 1 is the day of Vaccination 1.

Table 3. Derived Variables for Each Local Reaction Within the Time Interval

Variable ^a	Yes (1)	No (0)	Missing (.)
Any Day 1 to 10	Subject reports the reaction as “yes” on any Day 1 to 10.	Subject reports the reaction as “no” on all 10 Days (1 to 10) or as a combination of “no” and missing on all 10 Days (1 to 10).	Subject reports the reaction as missing on all 10 Days (1 to 10).

a. The variable will be derived for each of the local reactions (redness, swelling, and pain at the injection site) and for each of the severe or greater local reactions within Day 1 to Day 10 following Vaccination 1.

For any local reaction on any day, a similar rule applies as specified below in Table 4.

Table 4. Derived Variables for Any Local Reaction Within the Time Interval

Variable ^a	Yes (1)	No (0)	Missing (.)
Any Day 1 to 10	Subject reports any local reaction as “yes” on any Day 1 to 10.	Subject reports “no” on all 10 Days (1 to 10) or as a combination of “no” and missing on all 10 Days (1 to 10) on all 3 local reactions.	Subject reports all 3 local reactions as missing on all 10 Days (1 to 10).

a. The variable will be derived for any local reaction (any of redness, swelling, and pain at the injection site) and for any severe or greater local reaction within Day 1 to Day 10 following Vaccination 1.

Duration (From First Day to Last Day Reported)

The duration of each local reaction will be calculated as the number of days from the start of the first reported reaction to the resolution of the last reported reaction, inclusive. Resolution is defined as the last day on which the reaction is recorded in the e-diary if the reaction lasted 10 days or less, or the day the reaction ended if it continued beyond Day 10 (the latter will be collected on the CRF). If there is no known date when the reaction ended, then duration will

be missing (unknown). Subjects with no reported reaction have no duration because it is not applicable. Only reactions reported as “mild,” “moderate,” or “severe,” as defined in [Table 2](#), will be included.

Duration of reactions ≥ 21 measuring device units will also be compiled.

Duration (Total Days Reported)

The duration of each local reaction (total days) will be calculated as the number of days with the reported reaction. Resolution is defined as the last day on which the reaction is recorded in the e-diary if the reaction lasted 10 days or less, or the date the reaction ended if it continued beyond Day 10 (the latter will be collected on the CRF). If there is no known resolution day, then duration will be missing (unknown). Subjects with no reported reaction have no duration because it is not applicable. Only reactions reported as “mild,” “moderate,” or “severe” will be included.

Total days of reactions ≥ 21 measuring device units will also be compiled.

Onset

The onset day of each local reaction and any local reaction will be derived. Onset is defined as the first day of reporting any severity of “mild,” “moderate,” or “severe.”

For the onset day of each local reaction, if subjects report severity change of the local reaction, only the first day of reporting that specific local reaction will be counted.

For the onset day of any local reaction, the first day of reporting any severity of any local reaction will be counted.

CCI [REDACTED]

CCI [REDACTED]

[REDACTED]

[REDACTED]

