6.2. Visit 2 (Vaccination 2 – 28 to 35 Days After Visit 1)

Prior to vaccination:

- Ensure and document that all of the inclusion criteria and none of the exclusion criteria are met and that none of the temporary delay criteria are met.
- Measure and record the subject's oral temperature (°F/°C).
- Record nonstudy vaccinations and medications as described in [Section 5.10.3](#).
- Collect a blood sample of approximately 50 mL for immunogenicity assessments prior to vaccination.
- Review the subject's e-diary data and collect the e-diary. Collect stop dates of any e-diary events ongoing on the last day that the e-diary was completed and record stop dates in the CRF.
- Determine whether any AEs, SAEs, or NDCMCs have occurred since Visit 1 and follow up on any previously reported events to determine the outcome (ie, record stop dates or confirm if they are still continuing) and record as described in [Section 8](#).
- An unblinded site staff member will prepare the investigational product according to the IP manual.

After vaccination (including investigational product administration):

- The blinded/unblinded dispenser/administrator will administer a single 0.5-mL injection of investigational product into the deltoid muscle (preferably in the nondominant arm).
- Blinded investigator site staff will observe the subject for at least 30 minutes after investigational product administration for any acute reactions. Record any acute reactions on the AE CRF and on an SAE form as applicable.
- Remind the subject to contact the investigator or investigator site staff immediately if any significant illness or medical event (eg, emergency room visit or hospitalization) occurs during the study period.
- Remind the subject to use appropriate contraceptives until 28 days after vaccination, if applicable, and document the conversation and the subject's affirmation in the subject's chart.
- The investigator or an authorized designee completes the CRF.

6.3. Visit 3 (Follow-up Vaccination 2 – 28 to 35 Days After Visit 2)

- Ensure and document that all of the inclusion criteria and none of the exclusion criteria are met and that none of the temporary delay criteria are met.
- Record nonstudy vaccinations and medications as described in [Section 5.10.3](#).
- Perform a contraception check, if applicable, and document the conversation and the subject's affirmation in the subject's chart.
- Collect a blood sample of approximately 30 mL for immunogenicity assessments.

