7.1.1. Subject Electronic Diary

The subject will be asked to monitor and record local reactions for 10 days and systemic events and antipyretics/pain medication used to treat symptoms for 7 days, each evening following Vaccination 1 (Day 1 through Day 10 or Day 7, respectively, where Day 1 is the day of vaccination) on a system that uses a personal digital assistant (PDA) or other technology. This system, hereafter referred to as the subject's e-diary, allows recording of these assessments only within a fixed time window, thus providing the accurate representation of the subject's experience at that time. Data on local reactions, systemic events, and antipyretics/pain medication used to treat symptoms reported in the e-diary will be transferred electronically to the e-diary vendor, where they will be available for review by investigators, their qualified designees, and sponsor staff at all times via an internet-based portal. At intervals agreed to by the vendor and Pfizer, these data will be transferred electronically to Pfizer for analysis and reporting.

The e-diary data do not need to be reported by the investigator in the CRF. However, if a subject withdraws because of prompted events reported in the e-diary, the event(s) should be recorded on the AE page of the CRF, regardless of whether the investigator considers the event(s) to be clinically significant.

Investigators (or an appropriately qualified designee) are required to review the e-diary data online at frequent intervals (daily is optimal) to evaluate subject compliance and as part of the ongoing safety review.

The investigator or designee must obtain stop dates for any reactions ongoing on the last day that the e-diary was completed. The stop dates should be entered in the CRF at Visit 2.

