Oral temperature will be collected in the evening daily for 7 days following Vaccination 1 (Days 1 through 7, where Day 1 is the day of vaccination) and at any time during the 7 days that fever is suspected. Fever is defined as an oral temperature of $\geq 100.4^{\circ}\text{F}$ ($\geq 38.0^{\circ}\text{C}$). The highest temperature for each day will be recorded in the e-diary. In the event of a fever on Day 7, temperature will be collected daily until fever has resolved (1 day of temperature less than 100.4°F [38.0°C]) in order to collect a stop date in the CRF. Temperature will be measured and recorded to 1 decimal place and then grouped into ranges for the analysis according to Table 6 below:

Table 6. Ranges for Fever

100.4°F to 101.1°F (38.0°C to 38.4°C)
101.2°F to 102.0°F (38.5°C to 38.9°C)
102.1°F to 104.0°F (39.0°C to 40.0°C)
>104.0°F ($>40.0^{\circ}\text{C}$)

Maximum temperature range over Days 1-7 will be mapped into the ranges described in [Table 6](#).

Onset, duration, [CCI](#) will be calculated in the same way as for local reactions.

For each systemic event (each systemic event or fever), from Day 1 through Day 7, where Day 1 is the day of Vaccination 1, the following endpoints and variables will be derived for analyses following the same rules as for local reactions in [Section 3.3.1](#), where applicable:

- Maximum severity of each systemic event on any day (Day 1 to Day 7);
- Presence (yes or no) of each systemic event or fever on each day (Day 1 to Day 7);
- Presence (yes or no) of each systemic event or fever on any day (Day 1 to Day 7);
- Presence (yes or no) of any systemic event or fever on any day (Day 1 to Day 7);
- Presence (yes or no) of each severe (Grade 3, as defined in [Table 5](#)) systemic event on each day and on any day (Day 1 to Day 7);
- Duration of each systemic event or fever;
- Duration (total days) of each systemic event or fever;
- Onset day of each systemic event or fever;

[C](#)

[CCI](#)

For the purposes of deriving the variable “any systemic event” on any day (Day 1 to Day 7) or each day, the systemic events headache, fatigue, muscle pain, and joint pain will be included, and fever will be also included as one of the possible systemic events.

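### The SAP's duration rule does not match the protocol's trigger for collecting CRF stop dates, so some prompted-event durations are cut short or left ambiguous

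*SAP*

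**What the plan says.** SAP 3.3.1 defines two durations for each local reaction, first-to-last day and total days, and gives the same resolution rule under each. It has two branches. The first reads: "Resolution is defined as the last day on which the reaction is recorded in the e-diary if the reaction lasted 10 days or less". The second, in the first-to-last definition, follows in the same sentence: "or the day the reaction ended if it continued beyond Day 10 (the latter will be collected on the CRF". A further sentence covers unknown end dates: "If there is no known date when the reaction ended, then duration will" be missing. The local e-diary covers "redness, swelling, and pain at the injection site, from Day 1 through Day 10".

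The protocol decides which stop dates are collected. Section 7.1.1 says the investigator or designee "must obtain stop dates for any reactions ongoing on the last day that the e-diary was completed", to be entered on the CRF at Visit 2. Section 6.2 repeats this for all e-diary events, systemic as well as local: "Collect stop dates of any e-diary events ongoing on the last day that the e-diary was completed and record stop dates in the CRF".

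SAP 3.3.2 carries the rule to systemic events and fever, whose diary runs from Day 1 to Day 7. Onset and duration "will be calculated in the same way as for local reactions", and the list of derived variables follows the local rules where applicable. No Day 7 version of the cut-off is written. The same section has a fever present on Day 7 followed until it resolves, so that the CRF holds a stop date.

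SAP 6.1.1 describes the duration summaries again, for local and systemic events including fever. Total duration counts days beyond the close of the diary period. Maximum duration is the last event day minus the first plus one, with no diary cut-off stated.

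**The concern.** The protocol's trigger is the state of the event at the subject's final diary entry, whichever day that is. The SAP uses two other tests: the length of the reaction and whether it ran past a fixed study day. These do not match the protocol's trigger, and they are not complementary, because one is a length and the other a calendar day.

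A collected stop date can therefore go unused, and some reactions satisfy both branches with different answers. For a diary that stops early, the programmer needs the CRF stop date to establish that the reaction lasted no more than 10 days, and the rule then sets that date aside.

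At stake is the description of how long prompted reactions last, in a study whose primary objective is to describe safety. Where the rule clearly errs, it errs towards shorter reactions.

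**Working it through.** The plan gives no figure to reproduce. The check applies the rule to hypothetical events.

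**Inputs.** Diary windows are Days 1-10 (local, SAP 3.3.1) and Days 1-7 (systemic and fever, SAP 3.3.2). Duration = resolution day − onset day + 1. Branch 1 applies if the actual length is at most 10 days, and sets resolution to the last diary day with the event. Branch 2 applies if the event ends after Day 10, and sets resolution to the CRF end day. Systemic rows take Day 10 literally.

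| Hypothetical event | Onset-end | Last diary day with event | Actual length | Branch 1 | Branch 2 |
|---|---|---|---|---|---|
| Local, resolves inside a complete diary | 1-6 | 6 | 6 | 6 | does not apply |
| Local, longer than 10 days | 2-14 | 10 | 13 | does not apply | 13 |
| (a) Local, diary stopped early | 2-9 | 5 | 9−2+1 = 8 | 5−2+1 = 4 | does not apply |
| (b) Systemic, ends on Days 8-10 | 3-9 | 7 | 9−3+1 = 7 | 7−3+1 = 5 | does not apply |
| (c) Local, short but crosses Day 10 | 5-12 | 10 | 12−5+1 = 8 | 10−5+1 = 6 | 8 |
| Systemic, crosses Day 10 | 5-12 | 7 | 8 | 7−5+1 = 3 | 8 |

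**Rows 1 and 2** are handled correctly. In row 1 there is no stop date to ignore; in row 2 the CRF date is used.

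**Case (a)** loses 8 − 4 = 4 days. Protocol 6.2 and 7.1.1 require the stop date, but only branch 1 applies.

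**Case (b)** loses 7 − 5 = 2 days. For the same event, SAP 6.1.1 total duration would count Days 8 and 9 and give 7. If Day 10 is read as Day 7, branch 2 also applies and gives 7. The overlap remains, however: the event lasted 7 days, so a branch 1 limit of 7 days is met too and still gives 5.

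**Case (c)** is ambiguous. Both branches apply when end − onset + 1 ≤ 10 and end > 10. For onset on Days 1-10 this is possible from onset Day 2 onwards, with one possible end day for onset Day 2, two for Day 3, and so on up to nine for Day 10: 1 + 2 + … + 9 = 45 onset-end pairs. The largest difference between branches is 9 days (onset Day 10, end Day 19: 1 day or 10). Every pair meets at least one branch.

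**Overall size.** For case (a), the fall in mean duration is q × k, where q is the share of subjects with the reaction who are affected and k the days cut. The documents give neither. Purely as assumptions, q = 2% and k = 3 gives 0.06 days; q = 10% and k = 5 gives 0.50 days. This shows how the error scales and is not an estimate.

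**The case against.** The strongest reply is that the rule has a second branch, which uses the CRF date for reactions running past Day 10. A reader who stops at branch 1 might infer that CRF stop dates are discarded in general. The documents do not support that: a local reaction longer than 10 days takes its CRF date, and one that resolves within a complete diary has none. Case (c) is an ambiguity, not certain truncation.

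The systemic case also has a milder reading. Day 10 is simply the end of the local diary, SAP 3.3.2 restates the window as Days 1-7 and applies the local rules only where applicable, and the fever follow-up exists to provide a stop date. Changing Day 10 to Day 7 is the sensible interpretation, and SAP 6.1.1 points the same way. This stands as mitigation, but the plan does not say it. A reader might also infer that no systemic duration of 8 to 10 days could ever be reported. That is not so even on the literal text: an event on Days 4-12 also meets branch 2 and can be reported as 9 days.

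SAP 6.1.1 does not settle case (a). Its clause on total duration concerns days after the diary period closes, whereas this reaction ends on Day 9, inside the Day 1-10 period. Its maximum duration does not say whether the last event day comes from the diary or the CRF.

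Finally, early abandonment of the diary may be uncommon, since protocol 6.1 asks for frequent online review of diary compliance, ideally daily. The rule is the same in both groups, and no hypothesis test or decision rule depends on it. All of this limits the consequence; none of it makes the rule right.

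**Conclusion.** The point holds as a mis-keyed and overlapping rule. Read literally, it gives a wrong duration from data already collected in case (a), and in case (b) unless Day 10 is read as Day 7; it gives two answers in case (c). It also conflicts with SAP 6.1.1 for systemic events ending on Days 8-10.

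The effect is confined to descriptive duration summaries. A reader might infer that the primary safety results are biased, but the primary endpoints in SAP 3.1 are proportions of subjects with events, which do not depend on when an event ended. In the worked examples, (a) loses 4 days and (b) loses 2. The direction in the clear cases is always towards shorter durations. The effect on group means cannot be computed, because the documents do not give the number of affected subjects. The examples assume an event present on every day from onset to end.

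**What to change.** In both duration definitions of SAP 3.3.1, replace the two branches with one test: if the event was present on the last completed e-diary day, resolution is the CRF stop date; otherwise it is the last e-diary day with the event. Keep the existing rule that an unknown end date makes the duration missing. In SAP 3.3.2, state that the diary period ends on Day 7 for systemic events and fever. Align the wording of SAP 6.1.1 so that its maximum and total durations use the same resolution day. All six worked events then receive their actual length.

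Two limits apply. Do not use the CRF stop date for the duration of reactions of 21 measuring device units or more: it dates the end of the reaction, not the day it fell below 21 units. No change is needed for antipyretic or pain medication, because SAP 3.3.3 already confines that duration to Days 1-7.

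The cost is SAP wording and a small programming change. No new data are needed, and affected durations become longer.
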